10.1 Extent of Exposure

Total number of vaccinations (times) and total dose (mg) will be summarized with number of subjects, mean, standard deviation, median, minimum, and maximum by vaccination group.

* Total dose is defined as sum of study drug doses at each time point.

- Total Dose in Placebo / GLS-5310 0.6 mg / GLS-5310 1.2 mg (8W) / GLS-5310 1.2 mg (Re-vac.) = Dose at Baseline + Dose at Week 8
- Total dose in GLS-5310 1.2 mg (12W) = Dose at Baseline + Dose at Week 12

10.2 Adverse Events

An adverse event (AE) is defined as any unfavorable and unintended change in the structure, function, or chemistry of the body, or worsening of a pre-existing condition, temporally associated with the use of a product whether or not considered related to the use of the product.

Frequencies will be presented with respect to maximum severity and to strongest relationship to vaccination of the investigational product. Multiple occurrences of the same AE will be counted only once following a worst-case approach with respect to severity and relationship to vaccination of the investigational product.

Treatment-emergency adverse event (TEAE) refers to any AE that did not exist prior to vaccination of the investigational product, but that occurred after the initial vaccination of the investigational product, or a pre-existing condition that worsens after the initial vaccination of the investigational product.

Adverse drug reaction (ADR) is any noxious and unintended response to a medicinal product related to any dose, which a causal relationship between a medicinal product and an adverse event cannot be ruled out. An ADR includes reactions that represent an unexpected worsening of an existing medical condition. The following relationship categories will be considered as ADR:

- Probably related
- Possibly related

CONFIDENTIAL

A serious adverse event (SAE) is any AE that meets one of the following conditions:

- Death
- Life-threatening events
- An event requiring inpatient hospitalization or prolongation of existing hospitalization during the period of protocol defined surveillance (including any overnight stay in the hospital, regardless of the length of stay, even if the hospitalization is only a precautionary measure to allow continued observation).
NOTE: Evaluation in a physician's office, or at a hospital or other urgent care setting in an observational, non-admitted status regardless of the time period of observation, does not constitute an SAE
- Events resulting in congenital anomaly or birth defect
- Events that cause persistent or significant disability/incapacity or substantial disruption of the ability to conduct normal life functions
- Other important medical events that may not result in death, are life threatening, or require hospitalization, but are considered as serious by the Investigator. Examples of such medical events include anaphylaxis, new onset seizures

An Adverse Events of Special Interest is an enhanced disorder of the immune system relationship, and the following symptoms can be observed more closely.

- Documented vital sign showing respiratory rates is 30 breaths or greater per minutes, heart rate is 125 beats or greater per minute, SpO2 is 93% or less in indoor air, or PaO2 / FiO2 is less than 300 mmHg.
- Respiratory failure (In case of requirement for high flow oxygen, non-invasive ventilation, mechanical ventilation or ECMO)
- Shock (systolic blood pressure < 90 mmHg or diastolic blood pressure < 60 mmHg or requiring vascular inhibitor)
- Severe acute renal failure, liver or neurological dysfunction
- Intensive Care Unit (ICU) admission
- Death

TEAEs leading to vaccination discontinuation is defined as TEAE that Action taken with IP is stopping vaccination.

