8.1.2 Safety Evaluations

8.1.2.1 Adverse Events (AEs)

8.2.1.1 Definition of Adverse Events

An AE (also referred to as an adverse experience) is defined as any unfavorable and unintended sign, symptom or laboratory abnormality that is temporarily associated with the use of a drug or treatment and does not imply any judgement about causality. An adverse event can arise with any use of a drug or treatment regardless of route of administration, dose, and may be delayed after a drug or treatment has been discontinued. An adverse event is not the same as an “overdose”; an overdose is a dose-related event specifically caused by exposure to an increased amount of drug.

Adverse drug reactions (ADRs) are all adverse and unintended reactions that occur at any dose of a study drug, and the causal relationship with the study drug cannot be denied.

Adverse events of Special Interest (AESI) include enhanced disease of the immune system, and the following symptoms can be monitored more closely:

- Patient with documented vital signs with: respiratory rate of ≥ 30 breaths per minute, heart rate ≥ 125 per minute, SpO₂ of $\leq 93\%$ on room air, or PaO₂/FiO₂ of < 300 mm Hg.
- Respiratory failure (requirement for high-flow oxygen, non-invasive ventilation, mechanical ventilation, or ECMO)
- Shock (systolic BP of < 90 mm Hg, or diastolic BP < 60 mm Hg, or need for vasopressors)
- Significant acute renal failure, hepatic or neurologic dysfunction
- Admission to ICU
- Death

An unexpected AE is:

- Not identified in the IB or otherwise not expected from the characteristics of the clinical material
- Not listed at the specificity or severity that has been previously observed

Treatment emergent AEs (TEAE) include the following:

- Post-treatment complications that occur as a result of protocol mandated procedure
- Any pre-existing condition that increases in severity, or changes in nature during or as a consequence of the study drug, will also be considered an AE
- Complications and termination of pregnancy; see Section 7.1.8 for additional information.
-

Study related AEs do not include the following:

- Elective medical or surgical procedures
- Non-elective medical or surgical procedures (Medical or surgical procedure (e.g. surgery, endoscopy, extraction, blood transfusion); On the other hand, the conditions that led to these procedures are considered adverse events.

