8.1.2.1.7 Causal Relationship of Clinical Material to Adverse Events

A causally related AE is one judged to have a suspected relationship to the administration of the investigational agent. Conversely, an AE may also be assessed as not related to the investigational product. The Investigator is responsible for reporting adverse events and judging the relationship between the administration of the investigational product and an AE because the investigator is knowledgeable about the participant (e.g., medical history, concomitant medications), administers the investigational product, and monitors the participant's response to the investigational product. The Sponsor will assess the overall safety of the investigational product and determine whether expedited reporting to regulatory agencies is indicated.

Investigators should use their knowledge of the Study Participant, the circumstances surrounding the event, and an evaluation of any potential alternative causes to determine whether or not an adverse event is considered to be related to the study drug by the following criteria:

- Related – the Investigator considers that there is a causal relationship between the event and study drug;
- Probably related – the Investigator considers that there is a probability of a causal relationship of the event to the study drug
- Possibly related – the Investigator considers that there is a possible causal relationship of the event to the study drug
- Not related – the Investigator considers that the event has no relationship to administration of the study drug

The following guidance should also be taken into consideration:

- Temporal relationship of event to initiation of study drug;
- Course of the event, discontinuation of study drug, or reintroduction of study drug (when applicable);
- Known association of the event with the study drug or with similar treatments;
- Known association of the event with the disease under study (as applicable);

- Presence of risk factors in the Study Participant or use of concomitant medications known to increase the occurrence of the event

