10.2.1 Summary of Adverse Events

The following types of all AEs will be summarized with the number of subjects, incidence (%), 95% Clopper-Pearson's confidence interval and the number of events. In Phase IIa analysis, the differences in proportion between the groups will also be calculated with exact 95% confidence interval (Chan and Zhang 1999).

CONFIDENTIAL

The Solicited local AEs and Solicited Systemic AEs will be summarized for all TEAEs, all ADRs, all SAEs and all SADRs.

- TEAEs
- ADRs
- SAEs
- SADRs
- TEAEs leading to vaccination discontinuation
- Adverse Events of Special Interest

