10.2.2 Analysis Adverse Events

The following types of AEs will be coded with medical dictionary for regulatory activities (MedDRA) version 25.0 and will be summarized with system organ class (SOC) and preferred term (PT) by vaccination group using number of subjects, percentages, and number of events.

- TEAEs
- ADRs
- All Serious TEAEs
- Serious adverse drug reaction (SADR)
- All TEAEs leading to vaccination discontinuation
- Adverse Events of Special Interest
- TEAEs by severity (toxicity grade)
- ADRs by severity (toxicity grade)
- TEAEs by relationship to the investigational product
- Solicited local TEAEs
- Solicited local ADRs
- Solicited local SAEs
- Solicited local SADR
- Solicited systemic TEAEs
- Solicited systemic ADRs
- Solicited systemic SAEs
- Solicited systemic SADR

The details of SAEs will also be presented in a listing.

CONFIDENTIAL

The details of Solicited local/systemic SAEs will also be presented in a listing.

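### The SAP's list of causality categories counted as an ADR leaves out 'Related', so a literal reading under-counts ADRs and serious ADRs

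*SAP*

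**What the plan says.** Protocol 8.1.2.1.7 gives the investigator four causality categories: Related, Probably related, Possibly related and Not related. The first applies when "the Investigator considers that there is a causal relationship between the event and study drug". The protocol's section on the definition of adverse events (numbered 8.2.1.1) describes an ADR as a reaction for which "the causal relationship with the study drug cannot be denied".

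SAP 10.2 defines an ADR in nearly the same way, as a response for "which a causal relationship between a medicinal product and an adverse event cannot be ruled out". It then turns the definition into a data rule: "The following relationship categories will be considered as ADR", followed by two bullets, 'Probably related' and 'Possibly related'. 'Related' is not there. SAP section 12, which records changes to the protocol-specified analysis, does not mention the matter.

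The same section adds a counting rule: "Multiple occurrences of the same AE will be counted only once following a worst-case approach with respect to severity and relationship" to vaccination.

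The flag feeds two groups of outputs:

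- SAP 10.2.1 summarises ADRs and SADRs with incidence and Clopper-Pearson intervals. It adds that "In Phase IIa analysis, the differences in proportion between the groups will also be calculated with exact 95% confidence interval", and that "The Solicited local AEs and Solicited Systemic AEs will be summarized for all TEAEs, all ADRs, all SAEs and all SADRs".
- SAP 10.2.2 tabulates ADRs, SADRs, ADRs by severity and solicited ADRs and SADRs "by vaccination group using number of subjects, percentages, and number of events".

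**The concern.** SAP 10.2 gives two instructions for one flag, and they disagree on the strongest category. The definition takes 'Related' in; the list leaves it out. A programmer is more likely to code the list, because it is the part already expressed in data values.

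Safety is a primary objective in both phases. An error here runs in one direction only: it removes the events that investigators attribute most firmly to the vaccine, so the ADR and SADR rows can only understate harm. The report would also contradict itself, because the same events would still appear as 'Related' in the table of TEAEs by relationship.

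The point is limited to these outputs. Neither the halting rules in protocol 8.3.2 nor the Phase IIa entry criterion is worded with this list, and no claim is made about them.

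**Working it through.** **Step 1. Compare the scale with the list.**

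| Protocol category | Meets the ADR definitions? | On the SAP's ADR list? |
|---|---|---|
| Related | Yes: causality is affirmed, so it is neither denied nor ruled out | **No** |
| Probably related | Yes | Yes |
| Possibly related | Yes | Yes |
| Not related | No | No |

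The list and the definitions differ in one row only. Adding 'Related' makes the ADR set equal to every category except 'Not related', which is what both definitions describe. Nothing in the SAP text available restores the missing category.

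**Step 2. Illustrate the size.** The plan states no figure to reproduce and gives no event counts. The inputs are:

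- From the documents: 80 vaccine and 40 placebo participants in Phase IIa (protocol Table S1).
- Assumed: 48/80 vaccine (60%) and 8/40 placebo (20%) have at least one causally linked event; each such event is rated 'Related' with probability *p*; each affected participant has *k* such events, rated independently; *p* and *k* are the same in both arms.

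A participant disappears from the ADR count only if all of his or her causally linked events are rated 'Related', which has probability p^k. So

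reported incidence in the vaccine arm = 60% × (1 − p^k).

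| Events per affected participant | p = 0 | p = 0.25 | p = 0.50 | p = 0.75 |
|---|---|---|---|---|
| k = 1 | 60% | 45% | 30% | 15% |
| k = 2 | 60% | 56.25% | 45% | 26.25% |
| k = 3 | 60% | 59.1% | 52.5% | 34.7% |

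At k = 1, the largest loss, the Clopper-Pearson 95% intervals are:

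- 48/80 (no loss): 48.4 to 70.8%
- 36/80: 33.8 to 56.5%
- 24/80: 20.3 to 41.3%
- 12/80: 8.0 to 24.7%

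**Step 3. Between-group difference in Phase IIa.** It scales by the same factor: (60% − 20%) × (1 − p^k). At k = 1 it falls from 40 points to 30, 20 and 10 (for example 36/80 − 6/40 = 45% − 15% = 30). At k = 3 and p = 0.50 it is 40 × 0.875 = 35 points.

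**Step 4. Event counts.** The number-of-events column loses the whole share *p*, whatever the number of events per person.

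**Step 5. Serious ADRs.** These are likely to be few, so one event is enough to matter. One SAE rated 'Related' among 80 should give 1/80 = 1.25% (0.03 to 6.8%). The two-category list gives 0/80 (0 to 4.5%).

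**Step 6. Order of flagging and collapsing.** The SAP does not say whether the ADR flag is set before or after repeat occurrences are reduced to the strongest relationship. Under the two-category list, an AE rated once 'Possibly related' and once 'Related' is kept if flagged first and lost if collapsed first. Once 'Related' is listed, the order no longer affects ADR incidence. It can still affect ADRs by severity: with a Grade 3 occurrence rated 'Not related' and a Grade 1 occurrence rated 'Possibly related', collapsing first on both attributes gives a Grade 3 ADR, and flagging first gives a Grade 1 ADR.

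**The case against.** The best case on the other side is that this is a clerical slip with little practical effect. The definition stands directly above the list, and the list does not say that only those two categories count. A programmer would have to exclude the most certain category against that definition, and the quality control named in SAP Table 7 would have to miss it. Protocol 11.3.1 asks for TEAEs by severity and strongest relationship, serious AEs and administration-site events; it requires no ADR or SADR category. All of those outputs survive, so nothing is hidden. The SAP also calls the trial exploratory and descriptive. Finally, the table shells (SAP section 18) and the eCRF were not available and might define the category correctly.

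Much of this limits the consequence, and it is accepted: the loss needs literal programming and at least one event rated 'Related', and the events remain visible elsewhere. None of it removes the contradiction. A SAP should not depend on the programmer choosing the definition over the explicit rule. The ADR and SADR summaries are outputs the SAP itself specifies, with intervals and group comparisons. A correct definition in a shell or on a form would add a third statement without correcting this one. The objection that the illustrative rates have no source in the documents is right, and it is why they are labelled as assumptions and the zero case is shown.

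**Conclusion.** The concern holds. As written, the ADR list in SAP 10.2 is wrong: it omits a category that meets the ADR definitions of both documents, and following it gives wrong ADR and SADR counts whenever an event is rated 'Related'.

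The direction is certain and the size is not. Under the assumptions above, the understatement of ADR incidence in the vaccine arm runs from nil (no event rated 'Related') to 45 percentage points (60% reported as 15%, with one event per person and three quarters rated 'Related'). It shrinks quickly as events per person increase. The SADR row needs no such assumptions beyond a single serious event rated 'Related'. Because this is an unambiguous error in primary safety outputs and costs almost nothing to correct, it should be corrected before the analysis is run.

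**What to change.** In SAP 10.2, list 'Related', 'Probably related' and 'Possibly related' as ADR, or equivalently define ADR as any category except 'Not related'. Apply this to all ADR, SADR and solicited ADR and SADR outputs in 10.2.1 and 10.2.2. State that the flag is set on each AE record before repeat occurrences are collapsed, so that the by-severity tables are also unambiguous.

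SAP 4.1 describes the interim analyses as already performed. Check which list any existing ADR or SADR output used, and re-run it only if it used the two-category list.

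The cost is a line or two of SAP wording, one line of derivation code and a check of existing outputs. No new data are needed.

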10.2.1 Summary of Adverse Events

The following types of all AEs will be summarized with the number of subjects, incidence (%), 95% Clopper-Pearson's confidence interval and the number of events. In Phase IIa analysis, the differences in proportion between the groups will also be calculated with exact 95% confidence interval (Chan and Zhang 1999).

CONFIDENTIAL

The Solicited local AEs and Solicited Systemic AEs will be summarized for all TEAEs, all ADRs, all SAEs and all SADRs.

- TEAEs
- ADRs
- SAEs
- SADRs
- TEAEs leading to vaccination discontinuation
- Adverse Events of Special Interest

10.2.2 Analysis Adverse Events

The following types of AEs will be coded with medical dictionary for regulatory activities (MedDRA) version 25.0 and will be summarized with system organ class (SOC) and preferred term (PT) by vaccination group using number of subjects, percentages, and number of events.

- TEAEs
- ADRs
- All Serious TEAEs
- Serious adverse drug reaction (SADR)
- All TEAEs leading to vaccination discontinuation
- Adverse Events of Special Interest
- TEAEs by severity (toxicity grade)
- ADRs by severity (toxicity grade)
- TEAEs by relationship to the investigational product
- Solicited local TEAEs
- Solicited local ADRs
- Solicited local SAEs
- Solicited local SADR
- Solicited systemic TEAEs
- Solicited systemic ADRs
- Solicited systemic SAEs
- Solicited systemic SADR

The details of SAEs will also be presented in a listing.

CONFIDENTIAL

The details of Solicited local/systemic SAEs will also be presented in a listing.

10.3 VAS Scores

VAS score will be summarized by each timepoint using number of subjects, mean, standard deviation, median, minimum, and maximum by vaccination group.

10.4 Laboratory Evaluations

For numeric laboratory parameters that contain inequality signs in the results, only the numeric portion of the results will be used in the analysis removing the inequality signs (e.g., '<1.002' will be analyzed as '1.002').

Continuous parameters will be summarized by each timepoint and the changes from baseline to each timepoint using number of subjects, mean, standard deviation, median, minimum, and maximum by vaccination group.

Categorical parameters will be classified into Normal/NCS (not clinically significant) or CS (clinically significant) and the changes from baseline to each timepoint will be presented as a shift table by vaccination group.

Compare the laboratory results with the normal range will be classified into Low (<Lower limit), Normal(include normal range), High (>Upper limit) and the changes from baseline to each timepoint will be presented as a shift table by vaccination group.

The analysis units of laboratory parameters are as follows.

Table 5 Units of Laboratory Parameters

Hematology		Biochemistry	
Parameter	Unit	Parameter	Unit
RBC	$10^6/\mu\text{L}$	Glucose	mg/dL
Hemoglobin	g/dL	BUN	mg/dL
Hematocrit	%	Creatinine	mg/dL
Platelet	$10^3/\mu\text{L}$	Uric acid	mg/dL
WBC	$10^3/\mu\text{L}$	Total protein	g/dL
Neutrophil	%	Albumin	g/dL
Lymphocyte	%	Total bilirubin	mg/dL
Monocyte	%	ALP	IU/L
Eosinophils	%	AST	IU/L
Basophils	%	ALT	IU/L
		GGT	IU/L
		Total Cholesterol	mg/dL

CONFIDENTIAL

Hematology		Biochemistry	
Parameter	Unit	Parameter	Unit
		CPK	IU/L
		Na	mmol/L
		K	mmol/L
		P	mg/dL
		Cl	mmol/L
		Ca	mg/dL
		Mg	mEq/L

The details of parameters that are clinically significant after baseline will be presented in a listing with results for all timepoints.

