7.3.3 Adverse effects

Adverse effects that will be queried at each study visit include those related to the underlying disease and treatment, those potentially related to study drug, and those potentially related to study drug administration. AEs should be graded according to the "Toxicity Grading Scale for Healthy Adult and Adolescent Volunteers Enrolled in Preventative Vaccine Clinical Trials" issued in September 2007 by the US FDA (Appendix A). Subjects record the response (local and systemic) after vaccination on the evening of each vaccination day and 7 days after each vaccination day in the subject diary (Appendix B).

Subjects record the response to the injection site using the measurement tool provided, and the investigator reviews the subject diary. The response results described are evaluated for clinical significance and recorded as appropriate in the CRF.

Subjects who develop Grade 1 or higher eosinophilia (eosinophil count of ≥ 650 cells/mm³) will be asked to return weekly for repeat CBC determinations until resolution of the eosinophilia.

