8.1.2.1.6 Assessing Severity (Intensity)

The Investigator will grade laboratory AEs and clinical AEs (based on discussions with study participants) using the Toxicity Grading Scale for Healthy Adult and Adolescent Volunteers Enrolled in Preventive Vaccine Clinical Trials (Appendix A):

Adverse events will be recorded on the eCRF at the severity reported by the Investigator.

- Mild (Grade 1)
- Moderate (Grade 2)
- Severe (Grade 3)
- Potentially Life Threatening (Grade 4)

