8.1.5 Safety Laboratory Evaluations

Blood for a complete blood count with differential(RBC, hemoglobin, hematocrit, platelet, WBC, neutrophil, lymphocyte, monocyte, eosinophil, basophil) and chemistries (consisting of sodium, potassium, blood urea nitrogen (BUN), creatinine, glucose, ALT, and bilirubin, Ca, Cl, AST, ALP, CPK, albumin, total protein, total cholesterol) will be performed at Visits 1, 2, 4 and 8. A urine pregnancy test will be performed at Visit 1 and Visit 3 for those of childbearing potential. Laboratory test abnormalities are generally not recorded as adverse events or serious adverse

events. According to the judgment of the investigator, a clinically significant abnormal value is reported as an adverse event, and if it is related to a clinical adverse event, it is reported as the name of the adverse event. For laboratory test results, normal/abnormal evaluation is performed according to the normal range of the clinical trial site, and the severity is evaluated by the Toxicity Grading Scale.

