8.3.1 Events Requiring Expedited Reporting

Events requiring expedited reporting (ERER) are defined as any Adverse Events including:

- Grade 3 or greater systemic or local symptoms;
- Grade 3 or greater laboratory abnormalities
- Any episode of anaphylaxis or allergic reaction considered as study drug related or possibly study drug related

Sites will inform the Sponsor of any ERER within 24 hours, or increase of severity of an adverse event to Grade 3, to discuss whether dosing to the participant should continue.

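### SAP 10.4 plans no laboratory table by toxicity grade and carries eosinophils only as a percentage, so the protocol's 650 cells/mm³ threshold cannot be read from the planned laboratory tables

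*SAP*

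**What the plan says.** **Protocol.** Section 7.3.3 gives an absolute threshold and attaches follow-up to it: "Subjects who develop Grade 1 or higher eosinophilia (eosinophil count of ≥ 650 cells/mm³) will be asked to return weekly". Section 8.1.5 asks for two separate readings of each laboratory result. For the first, "normal/abnormal evaluation is performed according to the normal range of the clinical trial site"; for the second, "the severity is evaluated by the Toxicity Grading Scale". The same section says that laboratory abnormalities are not, as a rule, recorded as adverse events, but that "a clinically significant abnormal value is reported as an adverse event". Section 8.1.2.1.6 adds that "The Investigator will grade laboratory AEs and clinical AEs" on the toxicity scale. Section 8.3.1 puts "Grade 3 or greater laboratory abnormalities" among the events for expedited reporting. Table 8.1.2.1.3-1 lists eosinophilia among the solicited events, in the less common group.

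**SAP.** Table 5 fixes the analysis units: white cells in 10³/µL, and all five differential components, eosinophils included, in %. Table 4 (derived variables) contains no absolute differential count. Section 10.4 plans four outputs:

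- continuous summaries by timepoint, with change from baseline;
- a shift table of normal or not clinically significant against clinically significant;
- a second shift table: "Compare the laboratory results with the normal range will be classified into Low (<Lower limit), Normal(include normal range), High (>Upper limit";
- a listing of parameters that were clinically significant after baseline.

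Section 10.2.2 tabulates treatment-emergent adverse events and adverse drug reactions by toxicity grade.

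**The concern.** The protocol singles out one laboratory finding, gives it a numerical threshold and asks participants who cross it to return for repeat blood counts. A reader of the study report will want to know how many participants crossed it in each arm and how far. The SAP's laboratory tables use a different unit and a different classification, so they cannot answer. The same applies to grade generally: the protocol has laboratory severity graded, but no laboratory table shows the result. A participant could reach 650 cells/mm³, return weekly, be judged not clinically significant, and appear in no graded table. Safety is a primary objective, and the placebo comparison in Phase IIa would lose this information.

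**Working it through.** The documents state no figure to reproduce here. The check is a comparison of texts plus a unit conversion.

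**1. Does any planned output use grade or count?** Of the four outputs in SAP 10.4, the continuous summary uses the Table 5 unit (%), one shift table uses clinical significance, the other uses the normal range, and the listing is selected on clinical significance. None uses grade, for any parameter. None uses an absolute eosinophil count.

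**2. Can the percentage stand in for the count?** Since 1 mm³ = 1 µL, with white cells (WBC) in 10³/µL:

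count (cells/mm³) = WBC × 1000 × % / 100 = WBC × % × 10

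The percentage equal to the threshold is therefore 650 / (WBC × 10). The WBC values below are assumptions.

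| WBC (10³/µL) | Calculation | % equal to 650 cells/mm³ |
|---|---|---|
| 4 | 650 / 40 | 16.25 |
| 6 | 650 / 60 | 10.83 |
| 8 | 650 / 80 | 8.1 |
| 10 | 650 / 100 | 6.5 |
| 13 | 650 / 130 | 5.0 |

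**3. Can Low/Normal/High stand in for it?** The documents give no site ranges, so two upper limits are assumed. A value exactly at the limit is still Normal under the SAP wording.

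- Limit 5%: the limit corresponds to 5 × 4 × 10 = 200 cells/mm³ at WBC 4 and 5 × 11 × 10 = 550 at WBC 11. It reaches 650 only at WBC 13. A High result can therefore lie far below the threshold.
- Limit 8%: the limit corresponds to 8 × 4 × 10 = 320 at WBC 4, reaches 650 at about WBC 8.1, and is 8 × 11 × 10 = 880 at WBC 11. A Normal result can therefore lie above the threshold.

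Misclassification can run in both directions. Which direction dominates depends on site limits that are not stated.

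**4. Can the continuous summaries be combined?** No. They give WBC and eosinophil % separately, whereas the count is a product within each participant. A participant at 10% has 10 × 4 × 10 = 400 cells/mm³ if WBC is 4 and 10 × 10 × 10 = 1,000 if WBC is 10.

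**5. Would the weekly repeats reach the tables?** Those above the threshold "will be asked to return weekly for repeat CBC determinations until resolution of the eosinophilia". Under SAP 8.3 an unscheduled result is analysed only if it falls within a planned window and either fills an empty visit or lies closer to the planned day; otherwise it is only listed. In SAP Table 2 the Visit 2 window is days 5 to 9 and the next is days 53 to 59. After a finding on day 7, weekly repeats on days 14, 21, 28, 35, 42 and 49 all fall outside any window. Because repeats follow a count that has already crossed, losing them mostly hides the peak grade rather than the crossing itself.

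**The case against.** The strongest reply is that the SAP does what the protocol's statistical section asks. Protocol 11.3.2 wants continuous summaries, changes from baseline and percentages for categorical variables; SAP 10.4 gives these and adds shift tables. Protocol 8.1.5 concerns evaluation of results and 7.3.3 triggers repeat tests; neither prescribes a grade table. The trial is descriptive (SAP section 5). This stands: the SAP does not breach Protocol 11.3.2. It does not remove the gap between what the protocol has graded and what will be reported.

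A reader might also infer several stronger things that the documents do not support.

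- *That eosinophils are analysed only against site normal ranges.* SAP 10.4 also plans continuous summaries, a clinical-significance shift table and a listing.
- *That graded laboratory toxicity is not tabulated at all.* Abnormalities reported as adverse events enter the graded tables of SAP 10.2.2. Protocol 8.3.1 treats Grade 3 or higher laboratory abnormalities as adverse events for expedited reporting, so the higher grades should surface there. The gap is mainly at lower grades, where the 650 threshold sits.
- *That the percentage unit causes the missing grade table.* The grade table is absent for every parameter, whatever its unit. These are two separate gaps.
- *That the scale grades every cell type by absolute count.* The available text shows this only for Grade 1 eosinophilia; Appendix A is not part of it.
- *That the eosinophilic pneumonitis described in Protocol 1.1.1 makes this a product-specific alarm.* That passage concerns vaccines containing the nucleocapsid antigen. GLS-5310 encodes Spike and ORF3a (Protocol 6.1). The interest in eosinophilia rests on Protocol 7.3.3 and Table 8.1.2.1.3-1.

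The solicited-event listing does not clearly close the gap. Eosinophilia is found by blood test rather than by diary, the protocol table does not say whether it counts as local or systemic, and the SAP's solicited tables are not described as split by grade.

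**Conclusion.** The point holds in limited form. The planned laboratory tables cannot show how many participants reached 650 eosinophils/mm³, and graded laboratory findings are tabulated only when reported as adverse events. The percentage equivalent of the threshold ranges from 16.25% to 6.5% across assumed WBC of 4 to 10 ×10³/µL, so no single percentage cut-off reproduces it. The WBC values and upper limits are illustrative. The documents give no site ranges and no eosinophil distribution, so neither a misclassification rate nor the number of participants affected can be estimated. This is an inexpensive improvement to safety reporting and should be made. It does not affect the immunogenicity analyses.

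**What to change.** In SAP Table 4, add absolute eosinophil count = WBC × % / 100 in 10³/µL (× 1000 for cells/mm³), taken from the same sample. Do the same for any other differential component that Appendix A grades by count.

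In SAP 10.4, add two outputs by arm:

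1. The number and percentage of participants with any post-baseline count of at least 650 cells/mm³.
2. A shift table from baseline grade to worst post-baseline toxicity grade, for the parameters the scale covers. Baseline grade matters because exclusion criterion 19 removes only clinically significant abnormalities of Grade 2 or higher, so Grade 1 can be present at entry.

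Both should use all post-baseline results, including unscheduled and repeat tests, regardless of the visit windows in SAP 8.3. Placebo participants who later receive GLS-5310 should be shown separately after that point, in line with Protocol 11.8.

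The cost is one simple derivation for eosinophils plus programming to map each covered parameter to its grade. WBC and eosinophil % are already in Table 5, so no new data are needed.
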